To increase recruitment pool, an email blast will be sent out to an official VA mass email list that the recipients have consented to being on. This email group is specifically targeted towards veterans enrolled in healthcare in Indiana. The address is a no-reply address and veterans will be given only phone numbers for staff to protect their privacy.

To further increase recruitment, a single-slide informative visual will be placed on televisions in the Roudebush VAMC. This visual will include a graphic, a brief description of who would be eligible, a brief description of the commitment the study entails for the veteran, a brief description of the protocol, and contact information for the study team.

In addition to these measures, the study team will place lockboxes in the primary care clinics with a small advertisement for the study, using the same slide from the television ad.

The interested participants will be able to fill out an NDI at and place it in the lockbox. Study staff will collect these at the end of the day.

Randomization

Stratified and blocked randomization will be performed. After providing written-informed consent and completing their baseline interview, participants will be randomized to one of 2 arms:

- 1) Therapist-treated massage (TT-M)
- 2) Waitlist control (WL-C)

The randomization process will be directed by [name] (statistician) using statistical software with a random-number generator to create a list of group assignments before study recruitment begins. Randomization will be stratified by sex (men vs. women). Within strata, randomization with block sizes of 4 will be executed to ensure balance. Once an eligible participant has been screened, has signed informed consent, and has completed the baseline measures, the research assistant or project coordinator will pull the next sealed envelope. The randomization program locates the first unassigned record in the randomization list and assigns the participant to the group designated in that record. The participant identifier and date are written to the record. [name] will remain blinded to group assignment.

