8.0 Statistical Considerations

Sample size and power

The TOMCATT RCT was 'paused' on enrollment, study assessments, and massages in the TTM arm (massage arm) during an almost one year time period due to underlying safety concerns of trying to provide the intervention during the COVID-19 pandemic, although the control group was only 'paused' on enrollment. This impacted 16 patients enrolled in the TTM arm, of which 8/16 had completed their 1 Month assessment. The study will now be 'unpaused' for all, in which case new patients will be randomized and enrolled to the two study arms.

The primary intention-to-treat analysis will include all participants randomized and all assessments collected prior to pause for the TTM and all assessments for the waitlist control arm. Data will be analyzed as in the original analysis plan assuming data collection points were collected at TRT END and FOLLOW-UP on same time schedule (baseline, 1M, 3M, and 6M). Since 16 subjects were paused on their treatments and it has been over a year since they received a massage, for the primary analysis these patients will be considered lost-to-follow-up. Thus, we will recruit additional subjects to account for the increased LTF rate over what was originally expected due to COVID-19.

Original modification sample size: The modified study will focus on comparison of the TT-M and the waitlist control group (WL-C). We need 100 patients per group ($N = 200$) by 3 months to have 80% power to detect a 0.4 SD difference in change in NDI from baseline between TT-M and control with Type I error = 0.05 for the comparison of interest: TT-M vs WL-C. All analysis will be conducted under the intention-to-treat principle. Sample size was derived based on an independent two-sample t-test which is conservative compared to the contrast from our proposed linear mixed model.

Assuming total attrition for the TTM and WL-C arm is $(27+20)/(98+99) = 47/197 = 24\%$, we will seek to enroll a Total $N = 264$ ($200/.76$) or 132 per group in the TT-M and WL-C study groups. As we already have approximately 100 per group, with our current recruitment rate of 12 per month, we should be able to enroll an additional 64 subjects over 6 months.

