New modification sample size: For the comparison of the TT-M and the waitlist control group (WL-C) we need 100 patients per group ($N = 200$) by 3 months to have 80% power to detect a 0.4 SD difference in change in NDI from baseline between TT-M and control with Type I error = 0.05 for the comparison of interest: TT-M vs WL-C. All analysis will be conducted under the intention-to-treat principle. Sample size was derived based on an independent two-sample t-test which is conservative compared to the contrast from our proposed linear mixed model.

Previously we assumed a total attrition for the TTM and WL-C arm of $(27+20)/(98+99) = 47/197 = 24\%$, thus we sought to enroll a Total $N = 264$ ($200/.76$) or 132 per group in the TT-M and WL-C study groups. We will now enroll Total $N = 296$ ($264 + 16 \times 2$) so that we will

have an additional 16 in the TTM arm to account for the 16 that were paused due to COVID but will also maintain the current randomization allocation. For IRB purposes, we will continue to recruit to reach at most N = 308 this would increase the 16 COVID paused to also account for potential 24% attrition (16/.76 = 22 per group). However, this is not necessarily required as the COVID paused will still be included in the linear mixed model up until their one month assessment. This should allow us to reach our sample size of 100 per group to complete the 3 month assessment.

Data analysis: Baseline characteristics of TOMCATT sample

As an RCT, we expect characteristics of study participants to be balanced across the two study arms. We will compare all baseline demographic and clinical characteristics between the treatment groups using the appropriate test (ie, ANOVA, Kruskal-Wallis test, or Chi-square test). Variables found to significantly differ will be included in subsequent regression models.

Main analysis (Aim 1) of the primary outcome (NDI total score)

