Since this study is not specifically powered for secondary outcomes, these results should be interpreted cautiously. Pain intensity, pain interference, health-related quality of life (HRQL), depression, anxiety, and pain cognitions are all continuous measures. These subscales will be analyzed with the same approach as the primary outcome. For the pain intensity score, we will also report a clinically relevant descriptive statistic in which we define patients with > 30% reduction from baseline as "responders." For the NDI, a "responder" will be defined as a decrease of more than 5 points from baseline. This binary outcome will be observed at 1, 3, and 6 months (pre A033 only) for each participant. A generalized linear mixed model with predictors of group, time, and their interaction will be used that also includes a random subject effect to accommodate the potential correlation among observations from the same participant. The primary contrasts of interest will be the difference in proportions at 3 months between each treatment and the control group. We will use the Šídák method to adjust for multiple comparisons. Differences in proportions between treatment groups at the other time points will also be reported. For exploratory measures regression models will be used based on data type and will include pain coping, sleep problems, satisfaction, and social support.

Moderator analyses

As a secondary analysis for the primary outcome (NDI) as well as secondary outcomes, we will test baseline anxiety (GAD-7 and PTSD) and depression (PHQ-9) as moderators. This will be done separately for each potential moderator by re-running each mixed model for primary and secondary outcomes while additionally including the moderator, the moderator by treatment group interaction, and the moderator by treatment by time interaction. The treatment by time by moderator interaction represents the moderation effect on the treatment difference. If the treatment term is significant then moderation is occurring. Testing these measures as moderators will provide insight into generalizability of the interventions. For example, if the intervention loses effect in patients with high anxiety or depression, these patients may not be suited to the intervention.

Missing data

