We expect missing data in two different forms: missing by attrition and intermittent missing of observation. Attrition of < 15% is expected at the 3-month follow-up. We do not expect differential attrition between study arms. We will examine effects of missing observations due to attrition by examining patient characteristics associated with dropout. Factors associated with intermittent missing can similarly be identified. If missing data appears to be unrelated to any observed patient characteristics, and there are no obvious reasons to believe they are related to any unobserved characteristics, we will analyze the data under the assumption of missing completely at random (MCAR). If examination reveals observed factors are related to data missing, we will analyze data under the assumption of data missing at random (MAR). Multiple imputation techniques will be used to alleviate the impact of missing data. Importantly, the proposed mixed model methods for longitudinal data are appropriate if data are MCAR or MAR. However, if the pattern of missing data is nonignorable, more complex modeling approaches that model the missing data mechanism based on the EM algorithm or pattern-mixture models that include variables defined by the subject's pattern of missing data may be used. Finally, we will conduct sensitivity analyses to ensure the validity of study findings.

Data Collection for Aim 3

Aim 3 will examine the intervention implementation potential, including facilitators and barriers, and adherence, and intervention costs. Findings from this aim will help to maximize implementation potential and shorten the timeline to implementation in VA clinical settings.

Participants for Qualitative Interviews

For Veterans, the Aim 3 interviews will be conducted after the 3-month outcome assessment. We will purposefully sample Veterans with wide variations in change in pain disability (NDI total) from baseline to the 3-month assessment, and intervention adherence (e.g., number of massage sessions during the intervention period). Analysis will occur in parallel with data collection to allow sampling to theoretical saturation (i.e., no new properties, dimensions, or other qualities are seen in the data). Based on our experience and recommendations for qualitative sampling of subgroups, we expect to conduct up to 36 interviews.

Qualitative Interviews

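### The NDI responder model uses only yes/no change; imputing the NDI score by arm and then dichotomising would be a cheap improvement to this secondary analysis

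*Combined protocol and SAP*

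**What the plan says.** All of this is in section 8.0 of the combined protocol and SAP.

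- **Analysis of secondary outcomes (Aim 2).** An NDI responder is a patient whose score falls by more than 5 points from baseline. "This binary outcome will be observed at 1, 3, and 6 months (pre A033 only) for each participant". The model has group, time, their interaction and a random subject effect; baseline NDI is not named as a predictor. The main contrast is the difference in proportions at 3 months. A pain responder (more than 30% reduction) is also defined, but is called a descriptive statistic.
- **Sample size and power.** Sixteen patients in the therapist-treated massage arm (TT-M) were paused for COVID-19, and 8 of them had a 1-month assessment. "for the primary analysis these patients will be considered lost-to-follow-up". The text adds that "the COVID paused will still be included in the linear mixed model up until their one month assessment". The waitlist arm (WL-C) was paused on enrolment only. Sizing uses 47/197 = 24% attrition and then adds the 16 separately.
- **Baseline characteristics.** A baseline variable enters later models only if the arms differ significantly on it.
- **Missing data.** Attrition below 15% is expected at 3 months, with no difference between arms. Multiple imputation is to be used, and "the proposed mixed model methods for longitudinal data are appropriate if data are MCAR or MAR". The section does not say which outcomes are imputed, from which variables, or whether the score or the yes/no status is imputed.

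**The concern.** Responder status is a yes/no summary of change from baseline, so baseline cannot be a response occasion in this model. It can enter only if the significance rule for baseline covariates happens to select it. A patient with no follow-up score contributes nothing; 8 of the 16 paused patients are in this position. A patient seen at 1 month but not at 3 contributes only whether the 1-month fall exceeded 5 points. The baseline score and the size of the 1-month change are on file but unused.

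This matters in two ways. The unused scores predict 3-month status, so precision is lost. Also, a likelihood model is protected under MAR only with respect to the data it contains. If dropout depends on baseline NDI, the data are MAR given everything recorded, but not given the yes/no statuses alone. Patients with high baseline scores have more room to fall and tend to regress toward the mean, so they are more often responders. Losing more of them from one arm shifts the difference. The linear NDI model, with baseline among its repeated measures, does not have this weakness.

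The general promise of imputation could close the gap, but as written an analyst could fit the model to available data, impute status, or impute scores and then dichotomise, and choose after seeing the results.

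**Working it through.** **1. The plan's own figures.** Inputs: "Type I error = 0.05 for the comparison of interest: TT-M vs WL-C" and "80% power to detect a 0.4 SD difference in change in NDI from baseline between TT-M and control". Sidedness is not stated; two-sided is assumed. n per arm = 2 × (1.960 + 0.842)² / 0.4² = 98.1, rounded up to 99 (99.1 by the t-test); the plan uses 100, where t-test power is 80.4%. Then 200/0.76 = 263.2, so 264; 264 + 2 × 16 = 296, or 148 per arm. The ceiling is 16/0.76 = 21.05, taken as 22, and 264 + 44 = 308. All reproduce.

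**2. Patients with no 3-month score.** With attrition d and n per arm, the TT-M share is [16 + d(n − 16)]/n and the WL-C share is d. This takes the 16 as additional to the counted dropouts, as the sizing does, and carries their lost-to-follow-up status over to the responder analysis.

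| Attrition source | TT-M | WL-C | Overall |
|---|---|---|---|
| 24%, N = 296 | (16 + 0.24 × 132)/148 = 47.7/148 = 32.2% | 35.5/148 = 24.0% | 83.2/296 = 28.1% |
| 24%, N = 308 | (16 + 0.24 × 138)/154 = 31.9% | 24.0% | 27.9% |
| 27/98 and 20/99 (if listed in arm order), N = 296 | (16 + 36.4)/148 = 35.4% | 20.2% | 27.8% |
| 15% (upper limit in Missing data), N = 296 | (16 + 19.8)/148 = 24.2% | 22.2/148 = 15.0% | 58.0/296 = 19.6% |

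**3. Precision and bias by simulation.** The documents give no NDI mean, SD or correlation, so these are assumptions: baseline mean 18, SD 7, restricted to 10 or more (the entry criterion); between-visit correlation 0.5 or 0.7; a 3-month effect of 0.4 SD of change. There were 148 per arm, 16 paused TT-M patients (8 with a 1-month score), 24% attrition otherwise, and 600 trials per scenario. Dependent dropout has log-odds 1 per SD. Outside the 1-month-change patterns, half of ordinary dropouts also miss month 1. The stated model without imputation is compared with imputing NDI by arm from baseline and 1-month scores, then dichotomising. Bias is measured against the full data; all entries are percentage points, correlation 0.5 / 0.7.

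| Dropout depends on | Bias, stated model | Bias, impute then dichotomise | SD, stated model | SD, impute then dichotomise |
|---|---|---|---|---|
| Nothing (MCAR) | +0.2 / +0.1 | +0.1 / +0.2 | 6.55 / 6.23 | 5.80 / 5.66 |
| Baseline, same in both arms | −0.1 / −0.1 | −0.1 / 0.0 | 6.70 / 6.52 | 6.21 / 6.11 |
| Baseline, TT-M only | −3.2 / −2.4 | −0.3 / −0.2 | 6.43 / 6.30 | 5.77 / 5.90 |
| Baseline, opposite signs by arm | −5.7 / −3.9 | −0.3 / −0.1 | 6.56 / 6.68 | 5.94 / 5.93 |
| 1-month change, same in both arms | 0.0 / +0.2 | −0.1 / 0.0 | 6.62 / 6.05 | 5.89 / 5.37 |
| 1-month change, TT-M only | +1.5 / +1.5 | +0.1 / 0.0 | 6.89 / 6.49 | 6.15 / 5.89 |

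The full-data difference is 14 to 16 points, and the Monte Carlo error of the stated model's bias is about 0.15 point. Imputation lowers the SD by 9 to 11% under MCAR (5.80/6.55 = 0.89; 5.66/6.23 = 0.91) and by 6 to 11% across all rows.

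**4. Other assumptions.** With baseline SD 6, change SD 6.5 and responder rates of 50% and 35%, the SD falls from 6.35 to 5.72 points (10%). Against a true 15.5, the stated model gives 15.3 with equal baseline-dependent dropout. With log-odds of 0.5 or 1 per SD in TT-M and 0 in WL-C it gives 14.3 or 13.4; with ±0.5 of opposite sign, 13.6 or 17.4; with −1 in TT-M only, 17.6. That is a bias of about 1 to 2 points in either direction. A further check, with a saturated binary MAR estimator standing in for the mixed model, gave an SD reduction of 9 to 15% and a bias of 1 to 3 points.

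**5. Effect of the scoring rule.** Under MCAR, counting missing as non-response takes the full-data difference from 15.9 to 8.3 points (correlation 0.5) or from 14.3 to 7.7 (0.7). The stated model and score imputation both stay within 0.3 point of the full-data value.

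**The case against.** The strongest reply is that the plan already covers this. The Missing data section follows both outcome analyses, is not limited to the primary outcome, and commits to multiple imputation, with pattern-mixture or EM-based models if missingness is nonignorable, and to sensitivity analyses. That stands: a reader might infer that patients with missing scores have no provision at all, and the text does not support it. What is missing is the link to the responder endpoint and the choice between imputing score and status. It follows that the simulated figures describe the stated model without score-level imputation, which is one permitted reading of the plan.

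Three other stronger readings also fail.

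- A reader might take the phrase about each participant as a claim of complete data. It describes repeated measurement and leads into the random subject effect; the Missing data section openly expects missing values.
- A reader might infer that everyone without a 3-month score is dropped. Those with a 1-month status, including 8 of the 16 paused, still contribute it.
- A reader might take 28% overall as the expected loss. It rests on the sizing attrition; the under-15% figure gives at most about 20%.

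It is also fair that fitting a mixed model to responder status is standard practice, that a 10% gain in SD is an efficiency argument rather than an error, and that no passage proposes counting missing as non-response.

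**Conclusion.** The point holds as a cheap improvement to a secondary analysis. The NDI responder model leaves out baseline NDI and the continuous 1-month NDI of patients with no 3-month score: about 32% of TT-M and 24% of WL-C on the sizing figures, or at most about 24% and 15% on the Missing data figure plus the 16. Without score-level imputation, the SD of the 3-month difference is about 10% larger than needed. The bias is roughly 1 to 6 points if dropout depends on baseline NDI differently by arm, and about zero under MCAR or arm-symmetric dropout.

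These sizes rest on assumed NDI distributions and dropout strengths. The documents suggest unequal attrition by arm (the pause affected TT-M assessments only) but say nothing about its relation to baseline NDI, so a reader should not infer that the responder result will be biased. The plan says it is not powered for secondary outcomes and asks for caution in reading them. Pain response is labelled descriptive, and it is unclear whether the mixed model is meant to cover it. The primary linear NDI analysis is unaffected.

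**What to change.** In the Aim 2 and Missing data text of section 8.0:

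1. State that the NDI total score is multiply imputed, separately by arm, from baseline NDI, available follow-up NDI, sex and the characteristics found to predict dropout. Cover every randomised TT-M and WL-C patient, including the 16 paused patients, using their pre-pause data.
2. Derive responder status (a fall of more than 5 points) from the completed scores, and pool the 3-month difference in proportions with Rubin's rules.
3. Report missing as non-responder as a sensitivity analysis.
4. Score the descriptive pain responder rate (more than 30% reduction) in the same way, and say whether the mixed model applies to it.
5. Reconcile the 24% attrition used for sizing with the under-15% figure in the Missing data section.

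The cost is a few sentences and a little programming; no new data, visits or patients are needed. The downside is reliance on a stated imputation model. For the paused patients it assumes that, given their recorded scores, they would have resembled the other TT-M patients.

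### The moderator analyses run at least 21 significance tests with no stated level, family, hierarchy or exploratory label, so a chance moderator in one direction or the other is likely

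*Combined protocol and SAP*

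**What the plan says.** Under Moderator analyses in section 8.0, the plan states that "we will test baseline anxiety (GAD-7 and PTSD) and depression (PHQ-9) as moderators". It introduces this as a secondary analysis covering the NDI and the secondary outcomes. The tests are run one moderator at a time: "This will be done separately for each potential moderator by re-running each mixed model for primary and secondary outcomes while additionally including the moderator", together with its interactions with treatment and with treatment by time. The decision rule rests on significance: if a term is significant, moderation is taken to be present. The stated purpose is insight into generalizability, and the one illustration given is that "if the intervention loses effect in patients with high anxiety or depression, these patients may not be suited to the intervention".

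The section gives no significance level, no adjustment for the number of tests, no key test and no ordering. Šídák adjustment is mentioned twice in section 8.0, once under the Aim 1 analysis and once under the Aim 2 analysis. Neither mention defines a family of tests or refers to the moderator models. The Aim 2 text also asks for caution with secondary outcomes because the trial is not powered for them. It places pain coping, sleep problems, satisfaction and social support in an exploratory tier; the moderator tests are not placed there.

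**The concern.** Three moderators crossed with the primary and all secondary outcomes produce many interaction tests, each with its own chance of a false positive. A rule that declares moderation on significance alone, with no family defined, leaves the overall error rate uncontrolled. This holds even if every model is correctly specified and every interaction test has exactly its nominal size.

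The stake is a published statement about which Veterans benefit. The main comparison of massage with waitlist on the NDI is unaffected. However, a chance interaction could be reported as a limit on generalizability, and the plan's only worked illustration concerns patients with high anxiety or depression. Section 8.0 (Data Collection for Aim 3) also says the trial is meant to shorten the path to implementation in VA settings, so such a statement could carry weight.

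**Working it through.** **The plan's own figure.** The only Type I error stated is for the main comparison: "80% power to detect a 0.4 SD difference in change in NDI from baseline between TT-M and control with Type I error = 0.05". The normal approximation gives n = 2 x (1.960 + 0.842)² / 0.4² = 98.1, so 99 per arm; the t-test gives 99.1, so 100. The plan's 100 per group reproduces with a two-sided 0.05 (t-test power 80.4%). That level is given for massage versus waitlist on the NDI, not for the moderator tests. Using 5% per test below is therefore an assumption.

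**Number of tests.**
- Moderators: 3 (GAD-7, PTSD, PHQ-9).
- Outcomes: the NDI plus pain intensity, pain interference, HRQL, depression, anxiety and pain cognitions = 7.
- Tests: 3 x 7 = 21, taking one interaction test per model.

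Other counts can be defended. Dropping GAD-7 on anxiety and PHQ-9 on depression leaves 19. The Aim 2 list in section 2.0 (pain severity, HRQL, depression, anxiety, stress) gives 3 x 6 = 18. Adding the two responder outcomes to the seven gives 3 x 9 = 27. Counting HRQL subscales separately would give more.

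**Independent tests, no true moderation.**
- Either direction: 1 - 0.95^21 = 0.66. Expected false positives: 21 x 0.05 = 1.05.
- One direction: 1 - 0.975^21 = 0.41.
- Three NDI tests: 1 - 0.95³ = 0.14 in either direction; 1 - 0.975³ = 0.07 in one.

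**Correlated tests.** The documents give no correlations, so they are assumed: 0 to 0.7 between moderators and 0.3 to 0.7 between outcomes. Test statistics were simulated as multivariate normal (200,000 to 300,000 draws), with all outcomes scored in the same direction. The middle column uses 0.5 for both correlations.

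| Tests | Direction | 0.5 / 0.5 | Range |
|---|---|---|---|
| 21 | either | 0.49 | 0.35 to 0.61 |
| 21 | loss of effect only | 0.25 | 0.18 to 0.36 |
| 3 (NDI) | either | 0.125 | 0.11 to 0.14 |
| 3 (NDI) | loss of effect only | 0.06 | 0.06 to 0.07 |

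For the NDI rows only the between-moderator correlation matters. At 0.5 / 0.5, the either-direction figure is 0.45 for 18 tests, 0.47 for 19 and 0.56 for 27, so the conclusion does not depend on the exact count.

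**After adjustment.** For the three NDI tests the Šídák level is 1 - 0.95^(1/3) = 0.0170 each. The familywise rate is then 0.05 under independence and about 0.045 at a correlation of 0.5. Šídák over all 21 tests would need 1 - 0.95^(1/21) = 0.0024 each.

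**The case against.** The strongest reply is that the moderators are few, measured at baseline, named in advance and tested by interaction, and that the analysis is called secondary. Secondary-outcome results already carry a caution, and 18 of the 21 tests are on secondary outcomes. For the three NDI tests that the caution does not reach, the excess over 5% is modest. All of this stands and keeps the point in proportion. It does not replace a stated level and family: the caution is about power rather than multiplicity, and the plan has an exploratory tier it did not use here.

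It can also be argued that Šídák carries over because the models are re-run. The text leaves this open, so a reader who infers that each test is run at a full, unadjusted 5% goes further than the documents do; the level is unspecified. But an adjustment confined to each re-run model would still leave about 5% per model and would not control the error across 21 models. Only a family spanning the models would, and none is defined.

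Two stronger readings are tempting. One is that the plan commits to reading a positive result as showing who is unsuited to massage. It does not: the sentence is a conditional example, hedged with a may, and no eligibility or treatment rule follows from it. The other is that a false claim of that kind is about as likely as not. The 0.49 counts interactions in both directions, including massage working better in anxious or depressed patients. In the direction of the example the chance is about half that.

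**Conclusion.** The point holds as a gap in error control for the moderator analyses. Following the stated significance rule at a two-sided 5% per test, with no true moderation, the chance of some false moderator over 21 tests is about 0.49 (0.35 to 0.61), and about 0.25 (0.18 to 0.36) in the loss-of-effect direction. On the NDI alone it is 0.11 to 0.14 and 0.06 to 0.07. These figures rest on the assumed 5% level, on the count of 21 and on assumed correlations. Under every combination considered, the either-direction chance is well above 5%. The documents do not support even odds of a false statement that anxious or depressed patients are unsuited. The issue is worth correcting because the correction is cheap; it does not threaten the primary analysis.

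**What to change.** In Moderator analyses (section 8.0), state that all moderator tests are exploratory and hypothesis-generating, and report each as an interaction estimate with a 95% CI and no significance claim.

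If the sponsor wants to be able to make a moderator claim, limit it to the three interaction tests (GAD-7, PTSD, PHQ-9) on 3-month change in NDI, name that contrast, and apply the Šídák method the plan already uses, at 0.0170 per test. Moderator results on secondary outcomes stay exploratory. Make the example about patients who may not be suited conditional on that adjusted NDI test.

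The cost is a few sentences of SAP text, with no new data or patients. The price is lower power for each NDI moderator test (0.0170 instead of 0.05), in a trial sized only for the main NDI effect, and no moderator claim on any secondary outcome.
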